1.2 Study Objectives

Objectives	Endpoints
Primary Objective	Primary Endpoint
To evaluate and compare the change in morning oral malodor by an organoleptic assessment following 3 weeks of twice-daily tooth brushing using an experimental dentifrice containing 0.454% stannous fluoride and 0.3% zinc chloride compared to a standard fluoride dentifrice.	Change in mean organoleptic score from Baseline (pre-brushing) to 3 weeks (pre-brushing)
Secondary Objectives	Secondary Endpoints
Efficacy	
To evaluate and compare the change in morning oral malodor by VSC determination following 3 weeks of twice-daily tooth brushing using an experimental dentifrice containing 0.454% stannous fluoride and 0.3% zinc chloride compared to a standard fluoride dentifrice.	Change from Baseline (pre-brushing) to 3 weeks (pre-brushing) in: 
• Mean total VSC concentration in breath.• Mean hydrogen sulfide, methanethiol and dimethyl sulfide concentration in breath.
To evaluate and compare the change in oral malodor post brushing following 3 weeks of twice-daily tooth brushing using an experimental dentifrice containing 0.454% stannous fluoride and 0.3% zinc chloride compared to a standard fluoride dentifrice.	Change from Baseline (pre-brushing) to 3 weeks (1 hour post-brushing) in: 
• Mean total VSC concentration in breath.• Mean hydrogen sulfide, methanethiol and dimethyl sulfide concentration in breath• Mean breath organoleptic scores.
To evaluate and compare the change in oral malodor 1 hour post brushing at Baseline, and 1 hour post brushing following 3 weeks twice-daily use using an experimental dentifrice containing 0.454% stannous fluoride and 0.3% zinc chloride compared to a standard fluoride dentifrice.	Change from pre-brushing to 1 hour post brushing at Baseline and after 3 weeks in: 
• Mean total VSC concentration in breath.• Mean hydrogen sulfide, methanethiol and dimethyl sulfide concentration in breath.• Mean breath organoleptic scores.
Safety	
To assess the tolerability of an experimental dentifrice containing 0.454% stannous fluoride and 0.3% zinc chloride	
• Treatment emergent adverse events

This study will be considered successful if the experimental dentifrice containing stannous fluoride and zinc chloride demonstrates statistically significant greater reduction in total breath VSC compared to the reference dentifrice following 3 weeks of twice daily brushing.

1.3 Treatments

Table 1-2 presents the study products.

Table 1-2 Investigational/Study Product Supplies

Product Description	Experimental Dentifrice	Reference Dentifrice
	0.454% Stannous Fluoride dentifrice with 0.3% Zinc Chloride	Regular Fluoride Dentifrice
Product Name	N/A	Crest Cavity Protection (US Market Product)
Pack Design	One carton containing 2 overwrapped tubes of dentifrice	
Dispensing Details	Visit 2 (Baseline): 1 carton	
Product Master Formulation Code (MFC)	CCI	N/A
Dose/Product Application	Subjects will dose the toothbrush provided with a ribbon of paste to cover the brush head (a full brush head) on each brushing occasion	
Route of Administration	Oral topical use	
Usage Instructions	Subjects will brush twice daily (morning and evening) for 1 timed minute with their allocated product.	
Return Requirements	Used and unused study product to be returned to the sponsor.	

Detailed instructions for the return of study product/study supplies for the accountability checks and subsequent destruction which will be provided by the sponsor during the study in time for study close out visit.

1.4 Sample Size Calculation

Sufficient subjects will be enrolled to randomize approximately 106 subjects to have at least 100 complete the study (at least 50 subjects per treatment arm). It is considered sufficient to have 100 subjects complete in this study to meet the study's objectives. The subjects will be stratified by their sex prior to randomization. Existing GSKCH studies were referred to for information and data to enable calculation of an appropriate power and sample size however no relevant information was observed for a 3-week study in a gingivitis population as planned for this study.

Data from a published study that evaluated halitosis in subjects with gingivitis and periodontitis was taken into consideration to provide information regarding the variability and sample size for this endpoint. The sample size in this literature was N=116 for the gingivitis population and the variability estimate was observed to be 0.46 for the organoleptic score. The scoring was on a 5-point scale with very similar descriptors to those to be used in this study however only one assessor was used for organoleptic score assessment (as opposed to 3 assessors which will be used in this study). Considering the number of assessors in this study, the standard deviation (SD) was estimated to be 0.265 (0.46/sqrt(3)).

Using the SD of 0.265, for 50 subjects per arm (100 subjects completing the study) the detectable mean difference is estimated to be 0.15 for 80% power and alpha=0.05.

2 Planned Analyses

2.1 Interim Analysis

No interim analysis is planned.

2.2 Final Analyses

The final planned primary analyses will be performed after the completion of the following sequential steps:

1. All subjects have completed the study as defined in the protocol
2. All required database cleaning activities including any external data reconciliation have been completed and database has been locked.
3. All criteria for unblinding the randomization codes have been met and the randomization codes have been distributed.

3 Considerations for data analyses and Data Handling Conventions

3.1 Baseline Definition

For all endpoints, the baseline value will be the Day 0 (Visit 2) pre-brushing assessment with a non-missing value.

For secondary endpoints VSC and Organoleptic score, analysis is based on two baselines. One is as mentioned above Day 0 (Pre-brushing) and other is Week 3 (Pre-brushing).

3.2 Subgroups/Stratifications

Qualifying subjects will be stratified by the subject's sex and randomized to one of the two study treatments.

Two factors will be:

- Male
- Female

3.3 Centers Pools

Since this is a single center study, pooling of centres is not applicable.

3.4 Timepoints and Visit Windows

The timepoints and visits for this study are defined in the [Table 1.1](#) "Schedule of Activities". Any deviation from the study schedule may be reviewed on case-by-case basis at the Blinded

Data Review Meeting (BDRM) to determine whether the data should be excluded from the Per-Protocol (PP) population.

4 Data Analysis

Data analysis will be performed by PPD with oversight from GlaxoSmithKline Consumer Healthcare (GSK CH). The statistical analysis software used will be SAS version 9.4 or higher.

Prior to database closure a BDRM will be conducted in which various aspects of the trial will be discussed and agreed.

One aspect that will be considered prior to or during BDRM is the assessment of the number of subjects who have dropped or discontinued from the study due to pandemic related events (e.g., Coronavirus Disease of 2019 [COVID-19]) and the potential need of a sensitivity analysis. Any major changes to planned analyses will need an amendment to SAP.

Except as described below, all listings will be produced for all randomized subjects.

4.1 Populations for Analysis

Tables described in this section will be produced for all randomized subjects.

4.1.1 Subject Disposition

Screen failures are defined as subjects who consent to participate in the clinical study but are not subsequently randomized. An enrolled subject is a subject who has signed informed consent and is eligible to proceed beyond the screening visit.

The number of subjects screened, enrolled, and randomized will be presented in Table 14.1.1.

The number and percentage of screen failure subjects (subjects not randomized) with reasons why subjects are not randomized including percentage of subjects not randomized due to COVID-19 pandemic will also be displayed. Percentages for screen failure subjects will be based on the total number of subjects screened.

The number and percentage of randomized subjects who complete and discontinue the study, broken down by reason for discontinuation including percentage of subjects discontinued/withdrew from study due to COVID-19 pandemic, by study product and overall will also be displayed. The percentages will be based on the number of subjects randomized.

Table 14.1.1 will also present the number and percentage of subjects in each of the defined analysis populations (as defined in [Section 4.1.3](#)) by study product and overall. Percentages will be based on the number of subjects randomized.

Subject disposition including demographic data (age, sex, race and ethnicity), screening date, study product start date and time, subject status (completer, Yes/No), study completion /withdrawal date, duration (in days) in the study (defined as [(date of completion or withdrawal

GlaxoSmithKline Consumer Healthcare Confidential

CCI Statistical Analysis Plan Template v6.0

Page 12 of 31

– start date of study product use) + 1], and the primary reason for withdrawal will be listed (Listing 16.2.1.1) by study product.

Subject disposition information will be listed for non-randomized subjects (Listing 16.2.1.2), displaying subject number, demographic information (age, sex, race and ethnicity), enrolled [Yes or No], screening date, reason for screen failure and any further details of reason for screen failure and discontinuation status due to COVID-19 pandemic.

4.1.2 Protocol Deviations

Protocol deviations will be tracked by the study team throughout the conduct of the study. Data will be reviewed prior to unblinding and closure of the database to ensure all important deviations are captured and categorised. Subjects with important protocol deviations liable to influence the efficacy outcomes will be excluded from the PP population. Subjects may also be identified as having important protocol deviations not leading to exclusion from the PP population.

Important deviations of the protocol procedures may include, but will not necessarily be limited to the following:

- Consent procedures
- Inclusion/Exclusion criteria
- Study procedures
- Non-compliance with product administration
- Inadmissible concomitant medication

The specific details of the important protocol deviations will be listed in Protocol Deviation Management Plan and assessment process will be specified in the Blind Data Review Plan and subjects with important protocol deviations will be identified at the BDRM.

The number and percentage of subjects with at least one important protocol deviation, important protocol deviations not leading to exclusion from PP population with reasons for deviations and subjects with important protocol deviations leading to exclusion from the PP population with reasons for deviations will be presented by study product and overall (Table 14.1.2) and listed in Listing 16.2.2.1.

All protocol deviations collected on the protocol deviation case report form (CRF) page will be listed in Listing 16.2.2.2. The listing will present date of deviation, type of deviation and deviation description.

4.1.3 Analysis Populations

Three analysis populations are defined.

Population	Definition / Criteria	Analyses Evaluated
Safety	Comprise of all randomized subjects who complete at least one use of study product.	Safety

Population	Definition / Criteria	Analyses Evaluated
	
Any subject who receives a randomization number will be considered to have been randomized.
 
This population will be based on the treatment the subject actually received.
	
Modified Intent-To-Treat (mITT)	
Comprise all randomized subjects who complete at least one use of study product and have at least one post treatment efficacy assessment.
 
Any subject who receives a randomization number will be considered to have been randomized.
 
This population will be based on the study product to which the subject was randomized.
	Demographic Baseline Characteristics Efficacy Analysis
Per-Protocol	
Comprise all subjects in the mITT population who have at least one assessment of efficacy considered unaffected by protocol violations.
 
Protocol deviations that would exclude subjects from the PP population are defined in Section 4.1.2 (Protocol Deviations).
 
This population will be based on the study product to which the subject was randomized.
	Efficacy Analysis

NOTES :

Please refer to [Appendix 1](#): List of Data Displays which details the population to be used for each displays being generated.

The numbers of subjects included in each of the analysis populations will be summarized (Table 14.1.1). Subjects excluded from any of the analysis populations will be listed in Listing 16.2.3.1.

The primary population for assessment of efficacy will be the mITT Population. A PP analysis will be performed on the primary endpoint if there is more than 10% difference in the number of subjects between the PP and mITT populations. A decision on whether a PP analysis will be performed will be made prior to study unblinding (release of the randomization codes).

4.2 Subject Demographics and Other Baseline Characteristics

4.2.1 Demographic Characteristics

Descriptive statistics (number of subjects [n], mean, SD, median, minimum, and maximum for continuous variables and frequency count [n] and percentage [%] of subjects for categorical variables) will be presented for demographic variables by study product and overall. These variables include age, gender, race, and ethnicity and will be presented for the Safety population (Table 14.1.3.1) and the mITT population (Table 14.1.3.2).

Demographic information will be listed (Listing 16.2.4.1) for all randomized subjects.

4.2.2 General Medical History

Medical and surgical history (in the last year) including allergies or drug sensitivity will be listed in Listing 16.2.4.2, with start date and end date or ongoing at the start of study product.

4.3 Treatments (Study Product, Rescue Medication, other Concomitant Therapies, Compliance)

Randomization details will be listed, including the randomization number, stratification group, the planned study product, the actual study product the subject was randomized to and the randomization date (Listing 16.1.7.1) for all randomized subjects.

4.3.1 Study Product Compliance and Exposure

Compliance data will also be summarized for the mITT population and will be assessed by number of brushings over 3 weeks.

Number of brushings, brushing compliance (%), number of missed brushings, number of additional brushings will be summarized using descriptive statistics as separate categories by study product in Table 14.2.1 by cumulative visit.

Number of brushings is defined as: [(date of Visit 3 – date of Visit 2) multiplied by 2 – number of missing brushings + number of additional brushings].

Brushing compliance (%) is defined as: [100 x (Number of brushings / Expected number of brushings)], where expected number of brushings is defined as: [(date of Visit 3 – date of Visit 2) multiplied by 2].

Study product compliance (number of brushings / brushing compliance [%] / number of missed brushings / numbers of additional brushings) will be listed in Listing 16.2.5.1 for all randomized subjects by study product.

Supervised study product application (subject number, date of visit, supervised brushing completed? [Yes or No] and, date and start time of the supervised procedure/brushing) will be listed (Listing 16.2.5.2) for all randomized subjects.

4.3.2 Prior and Concomitant Medication

Prior medications/treatments, including prescription and non-prescription drugs, dietary supplements, and herbal remedies, taken in the last 28 days and prior to signing the informed consent form, will be documented in the CRF. The prior and concomitant medications will be coded using a validated medication dictionary, World Health Organization Drug Dictionary (WHODD).

Prior medications and prior non-drug treatments will be listed by subject, with drug name, WHODD Drug Synonym, reason, route, dose, frequency, start date and end date both relative to study product start date (Listing 16.2.4.3) for all screened subjects. Prior medications are defined as those which stopped before the first use of the study product.

Concomitant medications and concomitant non-drug treatments/significant non-drug therapies taken during treatment will be listed similarly (Listing 16.2.4.4) for all randomized subjects with either ongoing or end date displayed. Concomitant medications are defined as medications that started or stopped on or after the first use of the study product or are ongoing.

Unknown dates will not be imputed, however if the start or stop date is unknown, then it will be assumed to be concomitant medication unless the partial start date or stop date indicates differently.

4.4 Analysis of Efficacy

The primary population for assessment of efficacy will be the mITT Population.

4.4.1 Primary Efficacy Endpoint

4.4.1.1 Primary Efficacy Endpoint Definition

The primary endpoint for the study is the change in mean breath organoleptic score from Baseline (pre-brushing) to 3 weeks (pre-brushing) and the comparison between the Experimental and Reference Dentifrices in the mITT population.

Descriptive statistics (n, mean, SD, standard error [SE], median, minimum, and maximum) will be presented for mean breath organoleptic score at each assessment time point in Table 14.2.2.1.1 for all subjects in mITT population by study product. Raw means (\pm SE) of the mean breath organoleptic score at each time point will be plotted by study product in Figure 14.2.1.1 for all subjects in mITT population.

Individual breath organoleptic score data will be listed for each subject by visit and study product group in Listing 16.2.6.1 for all randomized subjects.

4.4.1.2 Statistical Hypothesis, Model, and Method of Analysis

Study product differences will be tested under the null hypothesis:

- H_0 : There is no treatment difference
- H_1 : There is a treatment difference

The following study product comparisons will be analyzed:

- Experimental Dentifrice versus Reference Dentifrice

An Analysis of Covariance (ANCOVA) model will be used to analyze the change in mean breath organoleptic score from baseline (pre-brushing) to week 3 (pre-brushing) with study product and gender as fixed effects and the mean baseline (pre-brushing) breath organoleptic score as a covariate. The least square means for each study product will be presented based on observed margins and used to test for < 0 change from baseline. The difference between least square means for the Experimental Dentifrice compared to the Reference Dentifrice will be presented and used to test for a difference between products. The two-sided p-values and 95%

confidence intervals (CIs) will be provided. This will be assessed at the two-sided 5% significance level.

Using the above model, adjusted mean change from baseline, along with 95% CIs will be reported by study product group and will be provided for mean breath organoleptic score in Table 14.2.2.2.1. Also, p-values testing for negative change from baseline will be presented for study product groups. Mean difference between study product groups, 95% CIs and p-values will be provided for mean breath organoleptic score in Table 14.2.2.2.1. This will be assessed at the two-sided 5% significance level.

The assumption of normality and homogeneity of variance in the ANCOVA will be investigated. In case of violation of these assumptions, a suitable nonparametric test (the Van Elteren test, adjusted for gender) will be performed, and results will be provided to support the ANCOVA results. If the inferences from the two analyses are similar, then both sets of results will be reported and emphasis will be made on the ANCOVA results. In case of discrepancies between inferences of the ANCOVA and non-parametric analysis, results will be drawn from the non-parametric analysis.

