12.3.1 Primary Analysis

The mean breath organoleptic score at a visit / time point will be derived across all of the recorded organoleptic scores recorded at the visit / time point.

The primary endpoint for the study is the change in mean breath organoleptic score from Baseline (pre-brushing) to 3 weeks (pre-brushing) and the comparison between the Experimental and Reference Dentifrices in the mITT population. This will be assessed at the two-sided 5% significance level.

An ANCOVA model will be used to analyze the change in mean breath organoleptic score from Baseline (pre-brushing) to 3 weeks (pre-brushing) with study product and gender as fixed effects and the mean Baseline (pre-brushing) breath organoleptic score as a covariate. The least square means for each study product will be presented based on observed margins and used to test for < 0 change from baseline. The difference between least square means for the

Experimental Dentifrice compared to the Reference Dentifrice will be presented and used to test for a difference between products. The two-sided p-values and 95% confidence intervals will be provided.

The assumption of normality and homogeneity of variance in the ANCOVA will be investigated. In case of violation of these assumptions, a suitable nonparametric test (adjusted for gender) will be performed, and results will be provided to support the ANCOVA results.

The mean pre-brushing breath organoleptic score values across the study and change from baseline will be summarised descriptively.

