4.4.2.2.1 Statistical Hypothesis, Model and Method of Analysis

Study product differences will be tested under the null hypothesis:

- H_0 : There is no treatment difference
- H_1 : There is a treatment difference

The following study product comparisons will be analyzed:

- Experimental Dentifrice versus Reference Dentifrice

A similar ANCOVA model as used for the primary analysis (as described in [Section 4.4.1.2](#)) will be used but with the appropriate pre-brushing and post-baseline result used accordingly.

Using the above model for each of the definition mentioned above, adjusted mean change from each baseline, along with 95% CIs will be reported by study product group will be provided for mean breath organoleptic score in Table 14.2.4.1 (with baseline as Day 0 pre-brushing) and

Table 14.2.4.2 (with baseline as Week 3 pre-brushing). Also, p-values testing for negative change from baseline will be presented for study product groups. Mean difference between study product groups, 95% CIs and p-values will be provided for mean breath organoleptic score in Table 14.2.4.1 (with baseline as Day 0 pre-brushing) and Table 14.2.4.2 (with baseline as Week 3 pre-brushing). This will be assessed at the two-sided 5% significance level.

The assumption of normality and homogeneity of variance in the ANCOVA will be investigated. In case of violation of these assumptions, a suitable nonparametric test (the Van Elteren test, adjusted for gender) will be performed, and results will be provided to support the ANCOVA results. If the inferences from the two analyses are similar, then both sets of results will be reported and emphasis will be made on the ANCOVA results. In case of discrepancies between inferences of the ANCOVA and non-parametric analysis, results will be drawn from the non-parametric analysis.

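### The nonparametric fallback for the organoleptic endpoints adjusts for gender but not for baseline score, so it usually has less power than a baseline-adjusted rank test; how much less depends on a correlation the plan does not give

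*SAP*

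**What the plan says.** The primary model in SAP 4.4.1.2 is an ANCOVA on change in mean organoleptic score, with study product and gender as "fixed effects and the mean baseline (pre-brushing) breath organoleptic score as a covariate". On the test level it says: "This will be assessed at the two-sided 5% significance level".

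If normality or homogeneity of variance is judged violated, the same section says "a suitable nonparametric test (the Van Elteren test, adjusted for gender) will be performed, and results will be provided to support the ANCOVA results". When the two analyses agree, emphasis stays on the ANCOVA. When they disagree, the conclusion is taken from the nonparametric test. SAP 4.4.2.2.1 repeats both the test ("a suitable nonparametric test (the Van Elteren test, adjusted for gender) will be performed") and the rule for the secondary organoleptic comparisons.

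Protocol 12.3.1 says "a suitable nonparametric test (adjusted for gender) will be performed", names no test, and gives it only a supporting role.

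Neither document says which variable is ranked (change or the Week 3 score), what counts as a violation, or what the correlation between baseline and Week 3 scores is expected to be.

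**The concern.** The two analyses use different covariate sets. A Van Elteren test is a stratified rank-sum test and has no place for a continuous covariate, so baseline score drops out exactly when the fallback comes into play. If change is ranked, baseline has been subtracted, but a chance baseline imbalance is not regression-adjusted and regression to the mean stays in the error. If the Week 3 score itself is ranked, baseline is not used at all.

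The fallback could well be used. The endpoint is a mean of about three whole-number grades from 0 to 5 (Protocol 9.2.2), so it moves in steps of about one third, and subjects must score at least 2 at baseline (Protocol 5.2, criterion 5e). A disagreement that comes only from losing the covariate would be read as a result of non-normality and could overturn the primary test.

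**Working it through.** **Inputs.** From SAP 1.4: 50 completers per arm, difference 0.15, SD 0.46/√3 = 0.2656 (the plan writes 0.265), power 80%, two-sided alpha 0.05. Assumed: rho. The plan also does not say whether 0.265 is the SD of change, of a single score, or of the ANCOVA residual, so all three readings are shown.

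**The plan's figure.** SAP 1.4: "Using the SD of 0.265, for 50 subjects per arm (100 subjects completing the study) the detectable mean difference is estimated to be 0.15". Check: (1.960 + 0.842) × 0.265 × √(2/50) = 0.148. Power at 0.15 is 80.8% by the normal approximation and 80.0% by noncentral t. The figure reproduces.

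**Formulas.** With equal variances and score SD s:
- SD of change = s√(2(1 − rho))
- SD after baseline adjustment = s√(1 − rho²)
- variance ratio, adjusted to change = (1 + rho)/2, that is 0.65, 0.75 and 0.85 at rho 0.3, 0.5 and 0.7.

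For rank tests under normality, use an effective n of 0.955 × 50 = 47.75 per arm.

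**Example: score SD 0.265, rho 0.5.**
- SD of change 0.265: 0.15/(0.265 × √(2/47.75)) − 1.96 = 0.81, power 79.0%.
- Adjusted SD 0.265 × √0.75 = 0.2295: 0.15/(0.2295 × √(2/47.75)) − 1.96 = 1.23, power 89.1%.
- Difference: about 10 points.

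**Analytic power, Van Elteren on change → baseline-adjusted ranks**

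| rho | 0.265 = SD of change | 0.265 = SD of score | 0.265 = residual SD |
|---|---|---|---|
| 0.3 | 79.0 → 92.9% (+14) | 64.7 → 82.6% (+18) | 60.6 → 79.0% (+18) |
| 0.5 | 79.0 → 89.1% (+10) | 79.0 → 89.1% (+10) | 66.8 → 79.0% (+12) |
| 0.7 | 79.0 → 85.1% (+6) | 94.6 → 97.2% (+3) | 72.2 → 79.0% (+7) |
| 0.9 | 79.0 → 81.0% (+2) | 100 → 100% (0) | 76.9 → 79.0% (+2) |

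**Simulation without the entry criterion** (4,000 normal trials per case, two equal sex strata, three SD readings). At rho 0.5 the gain is 8 to 10 points on continuous scores and 12 to 13 on scores rounded to thirds. Under the null, rejection was 4.6% to 5.5% for ANCOVA, Van Elteren and rank ANCOVA alike.

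**Simulation with the entry criterion.** Selecting on baseline shrinks its variance, so the formulas above no longer hold exactly. Here rho and SD describe the unselected population, baseline is cut at 2, the assumed pre-selection mean is 2.25, and errors are normal, heavy-tailed or skewed.

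| rho | Gain, scores in thirds | Gain, continuous scores |
|---|---|---|
| 0.3 | about 13 to 19 points | larger than at 0.5 |
| 0.5 | about 6 to 12 points | about 3 to 7 points |
| 0.7 | about 1 to 5 points | about −4 to +2 points |

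One case in full (thirds, normal errors, score SD 0.265, rho 0.5): ANCOVA 83%, Van Elteren 71%, rank ANCOVA 81%. In that case ANCOVA is significant and Van Elteren is not in at least 83 − 71 = 12% of trials. The rank ANCOVA is within 2 points of ANCOVA, so most of the loss comes from dropping baseline, not from using ranks. With a pre-selection mean of 2.0 the gain in this case falls to 5 points.

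**The case against.** The case for leaving the test alone has real content.

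- **A single figure for the loss is not supported.** A reader might infer a loss of about 10 points, or of at least 5 whenever rho is 0.5 or below. The first needs rho near 0.5, which the documents do not give. The second fails in some continuous truncated cases at rho 0.5. This stands, and only a range should be quoted.
- **Baseline is not ignored.** The endpoint is a change, so if change is ranked only the covariate adjustment is missing. This stands, subject to the SAP not naming the ranked variable.
- **The test is valid.** A reader might infer a type I error problem. The null results show none.
- **Van Elteren need not be weaker than the ANCOVA.** With continuous non-normal errors and selection at rho 0.5, Van Elteren had 94 to 97% power against 89 to 91% for ANCOVA (score SD reading), and ANCOVA alone was significant in only 1 to 5% of trials. This stands for that comparison. The fair comparator for the fallback is a rank test that keeps baseline, and that test was usually stronger.
- **The role is contingent.** The fallback needs a judged violation and decides only on disagreement; the protocol makes it supportive. This stands, but the SAP does let it decide.
- **Study success.** A reader might infer that the fallback can decide whether the study succeeds. The success statement (Protocol 3, SAP 1.2) rests on total breath VSC. The fallback bears on the declared primary endpoint, not on that statement.

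**Conclusion.** The point holds as one of efficiency and consistency. The fallback named in SAP 4.4.1.2 and 4.4.2.2.1 omits the baseline covariate that the ANCOVA uses, and the SAP lets it settle the inference when assumptions are judged violated and the analyses differ.

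On the scale actually used, with the entry criterion applied, the avoidable loss is likely to matter at rho 0.5 or below and to be small at rho 0.7. On continuous scores it is modest at rho 0.5 and absent, or slightly reversed, at rho 0.7. These sizes rest on an assumed rho, an assumed pre-selection baseline mean, and an SD whose meaning the plan leaves open. The change is worth making because it is cheap and the test can be decisive.

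**What to change.** In SAP 4.4.1.2 and 4.4.2.2.1, name a sex-stratified rank ANCOVA as the nonparametric test, and align Protocol 12.3.1:

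1. Within each sex, rank the post-baseline mean organoleptic score and the pre-brushing score that serves as baseline for that comparison (Day 0, or Week 3 pre-brushing for the Week 3 pre-to-post comparison).
2. Regress the first set of ranks on the second.
3. Compare products on the residuals with a sex-stratified Cochran-Mantel-Haenszel mean score test.

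This also settles which variable is ranked. Van Elteren can stay as an extra display.

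Cost: SAP and protocol wording and a few lines of SAS (PROC RANK, PROC REG, PROC FREQ), with no new data. Downsides: the method assumes a roughly linear relation between the ranks, gives only a p-value (as Van Elteren does), and gains little or nothing if rho is high.
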